## Division & Personnel

### Division

What Area Group does the PI belong to?

Epidemiology & Population Science

What Division/Department does the PI belong to?

Division of Translational Epidemiology

Within the division/department, what Center or group are you affiliated with, if any?

Substance Dependence Research Group

## Application for Continuation of Research

### Status

Current Status of Study:

All research interventions were completed. Only data analysis is ongoing.

### Summary of Experiences to Date

Please provide a summary of scientific progress of the study and the experience of research participants, to date. This requirement is designed to allow for the investigator and the IRB to reassess the study's risks and benefits in terms of developments in the field, changing practice patterns, and new IRB policies and procedures.

Recruitment and data collection are now complete. We had 45 individuals consent into the trial and 31 participants complete one or more study sessions. We have just completed data collection. Although we would have liked to continue recruitment to reach our n=60 goal, we were delayed in finding a clinic and launching data collection, had delays in recruitment efforts, and were only able to recruit about half of the desired sample size. The data have not yet been analyzed, but anecdotally, participants have told us that they have found the study to be helpful in decreasing their drinking. Although these comments often came from intervention participants, even some control participants expressed appreciation for the study, which got them to think about their drinking. We are requesting this continuation for data analysis only.

### Funding

Have there been any changes in funding status since the prior approval?

No

Have the principal investigator and other investigators made all required disclosures of financial interest in the study sponsor/product?

Yes

### Summary

Have there been any study findings, recent literature, or untoward events occurring here or at other sites in the past year which might affect the analysis of the safety, risks or benefits of study participation?

Yes

Please indicate how the new information affects the study's risk/benefit analysis and comment on whether consent form changes are necessary.

COVID-19 would raise risks for in-person data collection. Because of this, all study sessions have been conducted remotely, consistent with NYSPI guidelines, in response to the pandemic. No participant

activities have been done in-person since the NYSPI directive to shift to remote data collection. Data collection is now complete. No changes to the CF are indicated given that risks were minimized through a shift to remote research and because data collection is now complete.

Have there been any serious adverse events (serious and/or unanticipated problems involving risks to subjects or others at this site which occurred in the past year)?

No

Have all study staff with a significant role in the design or implementation of the human subject components of this study received required training in human research subject protections?

Yes

Is the study covered by a certificate of confidentiality?

Yes

Certificate expiration date (mm/dd/yyyy)

NA

## Overall Progress

Approved sample size

5 formative / 5 pretest / 80 trial

Total number of participants enrolled to date

5 formative / 7 pretest enrolled (5 completed baseline) / 45 trial

Number of participants who have completed the study to date

5 formative / 5 pretest / 31 trial (31 completed 1 or more study appts, 14 withdrawn/discontinued before baseline as detailed below, data collection now closed)

Have there been any significant deviations from the anticipated study recruitment, retention or completion estimates?

Yes

Describe actions taken or planned to address these problems.

For the trial we anticipated consenting n=80 participants of which n=60 would complete baseline. However due to delays in finding a clinic and in recruitment, and the impending end-of-grant, we were only able to consent n=45 into the study, of whom n=31 completed at least one study session. Although we made every effort to maximize our recruitment, we were unable to recruit more in the timeframe of grant funding.

Comments / additional information

The K23 grant was originally funded through 1/30/20, was extended to 6/30/20 in a first NCE, and is now extended until 9/30/20 through a second NCE. Although this will allow for time for data analysis, it does not accommodate continued recruitment.

## Sample Demographics

Specify population

formative research - HIV/HCV co-infected heavy drinkers

Total number of participants enrolled from this population to date

5 consented / 5 engaged in study sessions

Specify population #2

pretest - HIV/HCV co-infected heavy drinkers

Total number of participants enrolled from this population to date

7 consented / 5 engaged in study sessions

Specify population #3

trial - HIV/HCV co-infected heavy drinkers

Total number of participants enrolled from this population to date

45 consented / 31 engaged in study sessions

Gender, Racial and Ethnic Breakdown

Formative Research Participants (n=5)

	African Am/Black	Hispanic/Latino	White	Other/Multiple	Total
Male	5	0	0	0	5
Female	0	0	0	0	0
Transgender	0	0	0	0	0
Total	5	0	0	0	5

Pretest Participants (n=7)

\* One participant discontinued study.

\*\* One participant was withdrawn from the study.

	African Am/Black	Hispanic/Latino	White	Other/Multiple	Total
Male	6*	0	0	0	6
Female	1**	0	0	0	1
Transgender	0	0	0	0	0
Total	7	0	0	0	7

Trial Participants (consented n=45)

\* n=5 discontinued from study, n=2 withdrawn from study.

\*\* n=2 discontinued from study, n=1 withdrawn from study.

\*\*\* n=1 discontinued from study, n=3 withdrawn from study.

	African Am/Black	Hispanic/Latino	White	Other/Multiple	Total
Male	24*	6***	2	0	32
Female	11**	1	0	0	12
Transgender	1	0	0	0	1
Total	36	7	2	0	45

**Summary of Current Year's Enrollment and Drop-out**

Number of participants who signed consent in the past year

45

Did the investigator withdraw participants from the study?

Yes

Circumstances of withdrawal:

Participants consent into the study before completing final eligibility screening; their participation in the study is contingent on passing this final screening. Therefore, meeting exclusion criteria at this point requires withdrawing them from study participation.

Trial: One participant was disqualified from the study after health information request confirmed that participant did not have a history of Hepatitis C infection (an inclusion criterion), despite participant's initial self-report. Five participants were disqualified based on high-risk exclusion criteria, as assessed after consent per protocol (n=4 were at risk for alcohol withdrawal and n=1 affirmed anti-psychosis medication). Risk was assessed according to protocol, appropriate resources were provided, and no emergency referrals were needed.

Did participants decide to discontinue study involvement?

Yes

Circumstances of discontinuation:

Trial: Eight participants consented into the study but could not be scheduled for their baseline appointment despite repeated efforts to contact them and in many cases repeated no-shows. Aside from these 8 participants who did not attend baseline and the 6 withdrawn from the study (enumerated above), all participants completed baseline. Efforts were made to retain participants following baseline, but some were lost to follow-up because they either could not be reached, no-showed, or chose not to attend. However, 31 completed at least one study session. Data collection is now closed.

## Procedures

To create the protocol summary form, first indicate if this research will include any of the following procedures

- ✓ Psychiatric Assessment
- ✓ Collection of Biological Specimens
- ✓ Psychotherapy Trial
- ✓ Audio or Videotaping
- ✓ Internet-based Data Collection or Transmission

## Population

Indicate which of the following populations will be included in this research

- ✓ Adults
- ✓ Individuals with HIV/AIDS

✓ Substance Users

## Research Support/Funding

Will an existing internal account be used to support the project?

No

Is the project externally funded or is external funding planned?

Yes

Select the number of external sources of funding that will be applicable to this study

## Funding Source #1

Is the PI of the grant/contract the same as the PI of the IRB protocol?

Yes

Select one of the following

The grant/contract is currently funded

Source of Funding

Federal

Institute/Agency

National Institute on Alcohol Abuse and Alcoholism

Grant Name

Understanding and intervening with heavy drinking among patients with HIV and HCV

Grant Number

K23AA023753

Select one of the following

Single Site

Business Office

RFMH

Does the grant/contract involve a subcontract?

No

## Study Location

Indicate if the research is/will be conducted at any of the following

✓ NYSPI

✓ Other Columbia University Medical Center Facilities

This protocol describes research conducted by the PI at other facilities/locations

No

## Lay Summary of Proposed Research

---

## Lay Summary of Proposed Research

Among patients with HIV, especially those also infected with HCV, heavy drinking is associated with significant risks to health. However, little is known about how to best intervene with co-infected heavy drinkers, a particularly high risk group for whom targeted intervention has not been developed. Therefore, I propose to test a newly developed drinking-reduction intervention for patients with both HIV and HCV, which combines components of successful interventions developed for HIV and for liver disease patients.

We will recruit 80 HIV/HCV co-infected drinkers from HIV primary care in order to ensure 60 eligible and enrolled trial participants, which should yield an adequate final sample size of 45 participants completing the study. Participants will be randomly assigned to an intervention or control condition, while ensuring that equal numbers of individuals with alcohol use disorder are assigned to each condition. The intervention condition will receive brief in-person sessions with a counselor and will be asked to use a smartphone app daily to keep track of drinking and other health behaviors for two months. The intervention sessions will include information about HIV, HCV and alcohol, and the counselor will give the participant information about their liver function and alcohol use to try to motivate them to drink less. The control condition will simply be asked to drink less and will be given pamphlets with general information on HIV, Hepatitis C, and drinking from educational websites on HIV/HCV co-infection. We will then evaluate whether the intervention condition was more effective at reducing drinking than the control condition.

## Background, Significance and Rationale

### Background, Significance and Rationale

Patients with HIV have high rates of heavy drinking and alcohol problems, and face serious medical consequences from this use. Some research suggests that alcohol can increase viral load and decrease CD4 (cluster of differentiation 4; e.g., T helper cells) count, although this literature is conflicting. It also increases risk for liver damage, as does hepatitis co-infection, making liver disease a leading cause of death for patients with HIV. Patients with alcohol problems are also less adherent to antiretroviral therapy (ART), and some intentionally skip ART to try to avoid hepatotoxic effects of combining ART with alcohol. Some studies also show alcohol's interference with other aspects of engagement in HIV care.

Approximately 25% of HIV-infected patients are co-infected with HCV. Although HCV alone can lead to liver damage, HIV accelerates this progression, as does heavy drinking. Further, individuals with HCV who drink heavily may be less likely to access HCV medication. Despite serious health risks associated with alcohol use, some research suggests that HIV/HCV patients drink more than HIV mono-infected patients.

Growing recognition of alcohol-related harm in HIV patients has stimulated the development of drinking reduction interventions for HIV-infected heavy drinkers, some of which have been successful. Some interventions for HCV mono-infected drinkers and liver disease patients have also shown promise. Yet we know of no successful interventions that target HIV/HCV co-infected patients, a group with elevated drinking and particularly high consequences of drinking. Interventions for HIV patients address HIV health but do not address liver fibrosis, which is an urgent threat to survival for co-infected patients. Interventions for liver disease patients discuss fibrosis to motivate drinking reduction, but neglect HIV and important

topics such as ART adherence. Given that the drinking interventions for HIV and liver disease patients both effectively target drinking in medical patients, albeit through attention to different medical issues, such approaches can and should be integrated to provide an intervention that best meets the needs of patients with both HIV and HCV, a particularly high-risk group.

## Specific Aims and Hypotheses

### Specific Aims and Hypotheses

The aim is to pilot test a newly adapted intervention for HIV/HCV co-infected patients that integrates features from existing interventions for HIV patients and liver disease patients.

#### Primary Hypothesis:

At end-of-treatment (60 days) and 30 days after treatment (90 days), mean drinks per drinking day will be lower in the intervention (Clinician's Guide + HealthCall for HIV/HCV) than in the educational control condition.

#### Secondary Hypotheses:

At end-of-treatment (60 days) and 30 days after treatment (90 days), other measures of alcohol use (drinking frequency, maximum quantity, frequency of binge drinking and intoxication) will be lower, and readiness to change drinking and self-efficacy to change drinking will be higher, in the intervention (Clinician's Guide + HealthCall for HIV/HCV) than in the educational control condition.

#### Exploratory analyses:

Determine whether intervention efficacy differs between these with and without alcohol dependence, and between those with and without alcohol use disorder.

## Description of Subject Population

### Sample #1

Specify subject population

Formative Research - HIV/HCV co-infected heavy drinkers

Number of completers required to accomplish study aims

5

Projected number of subjects who will be enrolled to obtain required number of completers

5

Age range of subject population

18-99 (inclusive)

### Sample #2

Specify subject population

Pretest - HIV/HCV co-infected heavy drinkers

Number of completers required to accomplish study aims

5

Projected number of subjects who will be enrolled to obtain required number of completers

5

Age range of subject population

18-99 (inclusive)

### Sample #3

Specify subject population

Trial - HIV/HCV co-infected heavy drinkers

Number of completers required to accomplish study aims

We will recruit 80 participants to ensure that 60 meet eligibility criteria and agree to participate. A final sample size of 45 (assuming 75% retention from 60 enrolled patients) is adequate for detecting large differences ( $d=0.85$ ) with 80% power.

Projected number of subjects who will be enrolled to obtain required number of completers

80

Age range of subject population

18-99 (inclusive)

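### Should the 80% power statement based on 45 completers be revised now that at most 31 participants can supply outcomes?

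*Protocol*

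**What the plan says.** The Protocol's entry for the trial sample (Description of Subject Population, Sample #3) plans to recruit 80 people to obtain 60 enrolled, and then states: "A final sample size of 45 (assuming 75% retention from 60 enrolled patients) is adequate for detecting large differences", with d=0.85 and 80% power. The Lay Summary repeats the target, "which should yield an adequate final sample size of 45 participants completing the study". SAP 12.3.2.13 gives the same n, effect and power for the primary outcome, and 12.3.2.14 gives d=0.85 with 80% power for readiness to change and self-efficacy. The SAP is headed as an excerpt from a grant proposal finalized on May 6, 2014.

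The continuation section of the same Protocol reports what happened. Under Status: "Only data analysis is ongoing". Under Summary of Experiences to Date, the team "were only able to recruit about half of the desired sample size", and "The data have not yet been analyzed". Overall Progress gives the trial count as "31 completed 1 or more study appts, 14 withdrawn/discontinued before baseline as detailed below, data collection now closed". The drop-out summary adds that efforts were made to retain participants after baseline, "but some were lost to follow-up because they either could not be reached, no-showed, or chose not to attend".

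**The concern.** The power statement and the report of closed recruitment stand in one document, and they describe different trials. The planned figure rests on 45 completers, while no more than 31 people reached baseline.

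Even 31 is generous. Overall Progress lists it against the question on study completion but defines it as one or more appointments. The Primary Hypothesis concerns 60 and 90 days, so a person seen only at baseline supplies no primary outcome value. The number with a 60- or 90-day value is not given.

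Neither document restates the sensitivity for the smaller sample. A reader who took 80% power for d=0.85 at face value could give a null result more weight than it deserves.

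**Working it through.** **Inputs.** Planned: 60 enrolled, 75% retention, 45 completers, d=0.85, power 80% (Protocol, Sample #3; SAP 12.3.2.13). Equal allocation, about 30 per arm (Protocol, Intervention and Control groups). Alpha and sidedness are not stated; two-sided 0.05 is assumed. Achieved: 45 consented, 8 discontinued and 6 withdrawn before baseline (Protocol, drop-out summary).

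**Counts.** 60 × 0.75 = 45. 45 − 8 − 6 = 31. The trial footnotes in Sample Demographics agree. One cell reads "n=5 discontinued from study, n=2 withdrawn from study", and adding the other two gives 5+2+1 = 8 discontinued and 2+1+3 = 6 withdrawn. Applying the planned retention to the 31 gives 31 × 0.75 = 23.25, about 23; this is an assumption, not a reported count.

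**Reproducing the planned figure.** Two-sample t-test with noncentrality d × √(n₁n₂/(n₁+n₂)) and n₁+n₂−2 degrees of freedom. For arms of 22 and 23: 0.85 × √(506/45) = 0.85 × 3.353 = 2.850, df 43, power 79.6%. The normal approximation gives 81.3%. The stated 80% is correct. One-sided 0.05 would give 87.7%, so two-sided 0.05 is the reading that matches.

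**Same calculation at the smaller sizes.** For 15 and 16: 0.85 × √(240/31) = 0.85 × 2.782 = 2.365, df 29.

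| n (arms) | Power for d=0.85 | d detectable with 80% power |
|---|---|---|
| 45 (22/23) | 79.6% | 0.855 |
| 31 (15/16) | 62.8% | 1.04 |
| 23 (11/12), assumed | 49.3% | 1.23 |

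The near-equal splits of 31 and 23 are assumed and are the most favourable ones.

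**The planned analysis.** The SAP specifies mixed-effect GLMs, not a t-test, and gives no within-person correlation. Assume compound symmetry with correlation ρ of 0.3, 0.5 or 0.6. Relative to a single follow-up visit, the variance factor is:

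- single visit: 1; baseline-adjusted: 1−ρ²; change from baseline: 2(1−ρ)
- mean of 60 and 90 days: (1+ρ)/2; baseline-adjusted: (1+ρ)/2−ρ²; change: (1+ρ)/2+1−2ρ

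Dividing d by the square root of the factor (with one degree of freedom fewer when adjusted) gives 18 cases:

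| n | Power for d=0.85, range | Detectable d, range |
|---|---|---|
| 45 | 65–99% | 0.57–1.01 |
| 31 | 49–93% | 0.69–1.23 |
| 23 | 38–83% | 0.82–1.45 |

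At n=31, six cases reach 80%: the 60/90-day mean at ρ=0.3; the baseline-adjusted 60/90-day mean at all three correlations; the baseline-adjusted single visit at ρ=0.6; and change in the 60/90-day mean at ρ=0.6.

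In every case the detectable d at 31 is 1.22 times its value at 45. That is √(45/31) = 1.20 plus a small loss of degrees of freedom, so it restates the smaller n. At 23 the ratio is 1.43 to 1.44.

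**Precision around the prior effect.** The SAP says that a moderate effect would indicate promise even without significance, and cites d=0.44. Using 0.44 ± 1.96 × √(1/n₁+1/n₂+0.44²/(2n)):

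- n=45: standard error 0.302, interval −0.15 to 1.03, width 1.18
- n=31: standard error 0.364, interval −0.27 to 1.15, width 1.43

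Both intervals include zero, so the result at d=0.44 would have been uncertain at the planned size too.

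**The case for a change.** The strongest case for a change is that disclosing a recruitment shortfall is not the same as disclosing its effect on sensitivity. The Protocol is a continuation-stage document, so a dated line beside the power statement was possible, and the data had not yet been analysed. The line would cost little. It would not be power computed from the observed effect, which is uninformative; it would be a detectable effect at the achieved n for a difference fixed in advance. And a reader who sets 31 listed as completed against 45 planned completers would understate the loss, because the true counterpart of the 45 is unknown.

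Part of this stands. On the t-test that underlies the planning figure, sensitivity has fallen, and the count at 60 and 90 days is needed to read the results. But that count belongs in the results, where participant flow by arm and visit is ordinary reporting. The detectable-effect note is harder to defend. For the planned model it needs a correlation that the documents do not supply, and the plausible range is too wide to support one corrected figure. The SAP also allows non-normal outcome models, for which the d scale is only a proxy.

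**Conclusion.** No change to the plan. Four reasons together settle it.

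1. The Sample #3 entry answers a form question about how many completers the aims require. That is a planning quantity, the arithmetic behind it is right, and achieved numbers have their own fields elsewhere in the form.
2. The shortfall is stated and explained in Summary of Experiences to Date and Overall Progress. A reader of the Protocol could not suppose that 45 people completed.
3. The SAP dates itself to 2014, before recruitment, and could not carry achieved numbers.
4. Nothing downstream depends on the figure. Recruitment is closed, the model is unchanged, and the pilot's criterion of promise does not require significance.

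The size of the loss is clear only for the t-test: at most 62.8% power for d=0.85 and a detectable d of 1.04 at n=31, assuming two-sided 0.05 and near-equal arms. For the planned mixed model, power at 31 may lie on either side of 80%. Analysts will ordinarily report the numbers analysed by arm and visit and the planned-model estimate with its 95% confidence interval, which shows the achieved precision directly. The 45-completer figure should then be read as what was planned.

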### Gender, Racial and Ethnic Breakdown

I will recruit co-infected patients regardless of gender and race/ethnicity. We recently conducted a brief survey at the CUMC/NYP HIV clinic, which provides data on the expected demographic breakdown of the co-infected patients at this clinic. For those with HIV/HCV, 80% were male, 18% female, and 2% transgender, a realistic approximation of what to expect for this study. Of these co-infected participants (who were invited to endorse as many racial/ethnic identities as applied), 56% identified as Black, 26% as Hispanic, 15% as White, 10% as Native American, and 8% as Other, again a realistic approximation of what we can expect in the proposed study. We are also expecting to recruit co-infected patients through RecruitMe, Craigslist, and newspaper advertisements which will expand our recruitment catchment area to the entire NYC area and reflect greater diversity.

This largely mirrors nationally representative data published by the Centers for Disease Control and Prevention (CDC) on HIV-infected injection drug users (a close approximation of the HIV/HCV co-infected population), wherein 19% were female and 81% male, with a very similar racial/ethnic breakdown (48% Black, 27% Hispanic/Latino, 20% White, 5% other/multiple races). Therefore, we can have confidence that our results will be generalizable to the HIV/HCV co-infected population at large.

Description of subject population

The following table describes the types of participants that will be a part of each sample population. Each type of participant reflects the four recruitment methods we will use to identify patients for this study (see Recruitment Procedures).

Recruitment Method	Types of Participants	Study Population		
		Formative Research	Pretest	Trial
(1)	Patients who present to the CUMC/NYP clinic for care and are identified as potentially eligible by the recruiter and referred to the research team for formal screening	X	X	X
(2)	Patients identified as potentially eligible by the recruiter from a database (of previous participants interested in clinic research) and referred to research team for formal screening	X	X	X
(3)	Interested patients who call the research team directly for formal screening after referral from flyers or advertisements.	X	X	X
(4)	Interested patients in the NYC area who self-refer through RecruitMe and agree to be contacted by the research team for formal screening.			X

